6.4 Adverse Events (AE) and AE Management

6.4.1 Adverse Events (AEs)

The followings have been considered to be frequent or important AE according to previous studies:

Blood and lymphatic system disorders: anemia, neutropenia, thrombocytopenia, and febrile neutropenia

Gastrointestinal disorders: diarrhea, nausea, vomiting, abdominal ileus, and stomatitis

General disorders: Asthenia, fatigue, decreased appetite, mucosal inflammation, and pyrexia

Infectious disorders: Pneumonia, and urinary tract infection

Others: Dysgeusia, alopecia, and pulmonary embolism

MedDRA SOC Preferred Term	TAS-102 (N=335) n (%)		Placebo (N=168) n (%)	
	All Grades	Grade ≥ 3	All Grades	Grade ≥ 3
Blood and lymphatic system disorders				
Anaemia	149 (44.5)	63 (18.8)	32 (19.0)	13 (7.7)
Neutropenia	129 (38.5)	78 (23.3)	6 (3.6)	0
Leukopenia	57 (17.0)	23 (6.9)	3 (1.8)	0
Thrombocytopenia	33 (9.9)	7 (2.1)	2 (1.2)	0
Gastrointestinal disorders				
Diarrhoea	76 (22.7)	9 (2.7)	24 (14.3)	3 (1.8)
Nausea	124 (37.0)	10 (3.0)	53 (31.5)	5 (3.0)
General disorders and administration site conditions				
Fatigue	89 (26.6)	23 (6.9)	35 (20.8)	10 (6.0)
Investigations				
Neutrophil count decreased	51 (15.2)	38 (11.3)	1 (0.6)	0
White blood cell count decreased	23 (6.9)	9 (2.7)	0	0

MedDRA = Medical Dictionary for Regulatory Activities; N = total number; n = subset of total; SOC = system organ class

		Studies J003-10040030 and TPU-TAS-102-301 Combined			
		TAS-102 (N=646) n (%)		Placebo (N=322) n (%)	
MedDRA SOC Preferred Term		All Grades	Grade ≥ 3	All Grades	Grade ≥ 3
Blood and lymphatic system disorders					
Anemia		216 (33.4)	88 (13.6)	22 (6.8)	7 (2.2)
Neutropenia		156 (24.1)	107 (16.6)	0	0
Thrombocytopenia		37 (5.7)	11 (1.7)	1 (0.3)	1 (0.3)
Gastrointestinal disorders					
Diarrhea		213 (33.0)	23 (3.6)	45 (14.0)	1 (0.3)
Nausea		331 (51.2)	15 (2.3)	79 (24.5)	3 (0.9)
Vomiting		186 (28.8)	15 (2.3)	52 (16.1)	1 (0.3)
General disorders and administration site conditions					
Asthenia		97 (15.0)	18 (2.8)	30 (9.3)	8 (2.5)
Fatigue		246 (38.1)	25 (3.9)	82 (25.5)	16 (5.0)
Investigations					
Hemoglobin decreased		85 (13.2)	21 (3.3)	9 (2.8)	3 (0.9)
Hematocrit decreased		37 (5.7)	0	4 (1.2)	0
Lymphocyte count decreased		63 (9.8)	21 (3.3)	12 (3.7)	5 (1.6)
Neutrophil count decreased		229 (35.4)	142 (22.0)	2 (0.6)	0
Platelet count decreased		125 (19.3)	18 (2.8)	7 (2.2)	0
Red blood cell count decreased		39 (6.0)	0	2 (0.6)	0
White blood cell count decreased		232 (35.9)	87 (13.5)	3 (0.9)	0
Metabolism and nutrition disorders					
Decreased appetite		278 (43.0)	24 (3.7)	97 (30.1)	15 (4.7)
Nervous system disorders					
Dysgeusia		42 (6.5)	0	9 (2.8)	0
Skin and subcutaneous tissue disorders					
Alopecia		38 (5.9)	0	3 (0.9)	0

MedDRA = Medical Dictionary for Regulatory Activities; N = total number; n = subset of total; SOC = system organ class

Table 8. A summary of most frequently reported adverse events ($\geq 5\%$ in TAS-102 group that occurred twice or $\geq 5\%$ than placebo group) in previous randomized trials

6.4.2 Serious Adverse Events (SAEs)

Serious adverse drug reactions (SADR) were reported for 177 of 2066 patients (8.6%) with colorectal and gastric cancer who received TAS-102 35 mg/m²/dose monotherapy in unblended studies (see Table 9). The most commonly reported SADRs were febrile neutropenia (1.8%) and anemia (1.5%).

MedDRA SOC Preferred Term	n	%	Baseline ^b (N=2066)
Total number of subjects with serious adverse drug reactions	177	8.6	
Blood and lymphatic system disorders	89	4.3	
Anaemia	32	1.5	
Bone marrow failure	1	0.0	
Disseminated intravascular coagulation	1	0.0	
Febrile neutropenia	37	1.8	
Granulocytopenia	2	0.1	
Leukopenia	3	0.1	
Neutropenia	19	0.9	
Pancytopenia	12	0.6	
Thrombocytopenia	3	0.1	
Cardiac disorders	4	0.2	
Acute myocardial infarction	2	0.1	
Cardiorespiratory arrest	1	0.0	
Myocardial infarction	1	0.0	
Eye disorders	1	0.1	
Diplopia	1	0.1	
Gastrointestinal disorders	45	2.2	
Abdominal pain	4	0.2	
Anal fistula	1	0.1	
Ascites	1	0.1	
Colitis	2	0.1	
Constipation	2	0.1	
Diarrhoea	4	0.2	
Enterocolitis haemorrhagic	1	0.0	
Gastric haemorrhage	1	0.0	
Gastrointestinal haemorrhage	1	0.0	
Ileus	3	0.1	
Nausea	11	0.5	
Pancreatitis acute	1	0.0	
Small intestinal obstruction	3	0.1	
Subileus	1	0.0	
Vomiting	16	0.8	
General disorders and administration site conditions	12	0.6	
Fatigue	5	0.2	
General physical health deterioration	2	0.1	
Malaise	1	0.0	
Pyrexia	4	0.2	
Hepatobiliary disorders	3	0.2	
Cholangitis	1	0.0	
Liver disorder	1	0.0	
Liver injury	1	0.0	
Infections and infestations	34	1.6	
Atypical pneumonia	1	0.0	
Bacteraemia	3	0.1	
Biliary tract infection	1	0.0	
Cellulitis	1	0.0	
Cellulitis staphylococcal	1	0.0	
Clostridium difficile colitis	1	0.0	
Device-related infection	1	0.0	
Endophthalmitis	1	0.0	
Enteritis infectious	1	0.0	
Infection	2	0.1	

Lower respiratory tract infection	1	0.0
Neutropenic sepsis	4	0.2
Pelvic infection	2	0.1
Pneumonia	8	0.4
Pneumonia Klebsiella	1	0.0
Sepsis	2	0.1
Septic shock	3	0.1
Urinary tract infection	3	0.1
Urosepsis	1	0.0
Investigations	22	1.1
Blood bilirubin increased	3	0.1
Blood lactate dehydrogenase increased	1	0.0
Haemoglobin decreased	2	0.1
Neutrophil count decreased	8	0.4
Platelet count decreased	4	0.2
Weight decreased	2	0.1
White blood cell count decreased	8	0.4
Metabolism and nutrition disorders	12	0.6
Alkalosis hypochloraemic	1	0.0
Decreased appetite	7	0.3
Dehydration	6	0.3
Hypokalaemia	1	0.0
Hyponatraemia	1	0.0
Nervous system disorders	3	0.1
Cerebral infarction	1	0.0
Cerebrovascular accident	1	0.0
Transient ischaemic attack	1	0.0
Renal and urinary disorders	2	0.1
Acute kidney injury	2	0.1
Respiratory, thoracic and mediastinal disorders	1	0.0
Pulmonary embolism	1	0.0
Vascular disorders	1	0.0
Hypotension	1	0.0

MedDRA = Medical Dictionary for Regulatory Activities; SOC = system organ class

*Only includes serious adverse drug reactions from completed monotherapy protocols as of 24 Mar 2019:
10040010, 10040030, 10040040, TAS-102-101, TAS-102-102, TAS-102-103, TAS-102-104, TAS-102-108,
TAS-102-301, TAS-102-302, 10040090, 10040100, TAS-102-106, and TAS-102-401.

Note: Includes TAS-102 studies investigating 35 mg/m²/dose monotherapy in patients with colorectal and gastric cancer. Study medication-related adverse drug reactions are those adverse events considered by either the investigator or the sponsor as not denied, possibly related, probably related, and definitely related to TAS-102. Patients are counted at most once for each preferred term and each SOC. Inclusion in this table is subject to medical judgment.

Table 9. TAS-102 Baseline Frequency Serious Adverse Drug Reactions by System Organ Class and Preferred Term in Patients Receiving TAS-102 Monotherapy (Based on SAE Database)— Data Cutoff 24 Mar 2019

6.4.3 Management of AEs

All TAS-102-related toxicities should be treated with supportive care measures and symptoms managed as clinically indicated or local institutional practice. The criteria in this protocol regarding modifications of TAS-102 (dose interruption, reduction, resumption, and permanent discontinuation) should be followed closely.

6.4.3.1 Hematologic Toxicities

Patients should be informed of the possibility of severe infection related to myelosuppression and advised to promptly report any signs of infection such as fever to the treating physician.

Patients with low WBC counts and low neutrophil counts should be monitored carefully for infection and treated as medically indicated (e.g., with antibiotics, granulocyte-colony stimulating factor). Patients with thrombocytopenia and/or anemia should also be closely monitored for complications and provided treatments as clinically indicated. TAS-102 dose should be modified as recommended in the protocol.

6.4.3.2 Gastrointestinal Toxicities

Patients with nausea, vomiting, diarrhea and other gastrointestinal toxicities should be carefully monitored. Appropriate measures such as antiemetic, antidiarrheal, and/or fluid replacement therapy should be administered as clinically indicated. In addition, dehydration and any associated electrolyte disturbances should be prevented or corrected at onset. TAS-102 dose should be modified as recommended in the protocol.

7 FOLLOW UP AND OUTCOME EVALUATION

7.1 Follow-Up Schedule

The study assessments are described by procedure in the following sections. The study schedule must be followed with a window of +/- 3 days which is allowable for study procedures, as long as the proper order is maintained, and a window of +/- 7 days is allowable for CT scans and follow-up visits. During the baseline period, these windows are not applicable. Patients should be followed-up for up to 2 years.

7.2 Study Procedures

7.2.1 Informed Consent

Obtain signed and dated ICF from the patient prior to the implementation of study procedures required by the protocol. A copy of the signed and dated ICF should be given to the patient.

7.2.2 Medical History

Obtain a complete medical history at Baseline within 28 days prior to study medication administration.

7.2.3 Diagnostic Confirmation

Obtain histological, cytological or radiological confirmation of pancreatic cancer via radiological and pathology report at Baseline.

7.2.4 Physical Examination

Perform a complete physical examination at the time points listed below:

- Baseline within 7 days prior to study drug administration on Day 1 of Cycle 1.
- Beginning with Cycle 2, obtain within 24 hours prior to study drug administration.
- End of Treatment Visit.
- 30-day Safety Follow-up Visit.

7.2.5 Baseline Signs and Symptoms

Baseline signs and symptoms present within 28 days prior to study drug administration on Day 1 of Cycle 1 should be recorded in the patient's source documents.

7.2.6 Electrocardiogram

A 12-lead resting electrocardiogram (ECG) within 28 days prior to study drug administration on Day 1 of Cycle 1 should be obtained and recorded in the patient's source documents.

7.2.7 Height, Vital Signs, and Weight

Obtain the patient's height at Baseline within 7 days prior to study drug administration on Day 1 of Cycle 1. Collect the patient's vital signs (blood pressure, heart rate, body temperature, and respiration rate) and body weight at the time points listed below. Obtain all the vital signs in a position that is consistent for all time points for each patient.

- Baseline within 7 days prior to study drug administration on Day 1 of Cycle 1
- Beginning with Cycle 2, obtain within 24 hours prior to study drug administration
- End of Treatment Visit
- 30-day Safety Follow-up Visit

7.2.8 Performance Status (ECOG)

Obtain an ECOG performance status score at the following time points:

- Baseline within 28 days prior to study medication administration on Day 1 of Cycle 1
- On Day 1 of Cycle 1
- Beginning with Cycle 2, obtain within 24 hours prior to study drug administration
- End of Treatment Visit
- 30-day Safety Follow-up Visit

7.2.9 Hematology, Biochemistry, and CA 19-9

Collect blood for hematological, biochemistry and CA 19-9 assessments at the following time points and when clinically indicated:

- Baseline within 7 days prior to study drug administration on Day 1 of Cycle 1
- On Day 15 of Cycle 1
- Beginning with Cycle 2, obtain within 24 hours prior to Day 1 study drug administration and on Day 15
- End of Treatment Visit
- 30-day Safety Follow-up Visit

7.2.10 Urinalysis

Collect urine samples for qualitative (dipstick) analysis, to include tests for protein, glucose, urobilinogen, RBC, and WBC, at the time points listed below:

- Baseline within 7 days prior to study drug administration on Day 1 of Cycle 1
- Or clinically indicated

7.2.11 Pregnancy Test

For females of childbearing potential, collect urine samples for qualitative (dipstick) analysis, to include tests for protein, glucose, urobilinogen, RBC, and WBC, at the time points listed below:

- Baseline within 7 days prior to study drug administration on Day 1 of Cycle 1

7.2.12 Tumor Measurement

Tumor assessments/imaging studies of the chest, abdomen, and pelvis (as clinically indicated) must be obtained at each time point listed below for all patients.

- Baseline within 28 days prior to Day 1 Cycle 1
- Every 8 weeks from the start of treatment
- Within 2 weeks of the End of Treatment Visit if the patient has discontinued treatment for reasons other than radiologic disease progression. If an End of Treatment visit is not performed, tumor measurements must be obtained at the time the patient is discontinued from treatment.
- For patients that discontinued treatment for reasons other than radiologic progression, every 8 weeks during the follow-up period until the patient develops radiologic progression or the start of new anticancer treatment.

On-site tumor assessments will be performed by the Investigator/local radiologist according to RECIST criteria (version 1.1). Results of these assessments including response for target and non-target lesions and appearance of new lesions will be the basis for the continuation or discontinuation of study medication.

If the Investigator determines that a patient develops clinical progression manifested by symptomatic deterioration but not supported by radiologic evidence of progression, the patient should stop treatment. Symptoms of clinical progression must be documented in the patient's source documents. Every effort should be made to document objective progression even after discontinuation of treatment.

If a patient is withdrawn due to radiologic disease progression, additional CT scans are not required at the End of Treatment Visit. The same method of assessment and the same technique must be used to characterize each identified and reported lesion at Baseline, throughout the study, and during the follow-up period.

All patients' files and radiological assessments must be available for source verification. Results of any unscheduled evaluations should be recorded.

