4 STUDY SCHEMA

Safety monitoring will begin at the time the Informed Consent Form (ICF) is signed and continue for 30 days after the last dose of study medication or until the initiation of another cancer therapy, whichever comes first.

At the end of treatment, all patients will be followed for survival at scheduled 8-week time intervals until 2 years.

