Appendix 1. STUDY SCHEDULE

	Baseline Period		On Treatment Period (+/-3 days for procedures; +/-7 days for CT scans & FU)							End of Treatment Period (q8wk)		
	Baseline Day		Cycle 1				Subsequent Cycles			End of Treatment	30-day Safety FU	Survival FU
	-28 to -1	-7 to -1	1	12	15	End of recovery	1	12	15			
Procedure	x											
Sign ICF	x											
Enrolment	x											
Medical History	x											
Physical Examination		x					x			x	x	
Baseline signs and symptoms	x											
ECG	x											
Vital signs, height, body weight		x					x			x	x	
ECOG performance status	x		x				x			x	x	
Hematology		x			x		x		x	x	x	
Serum chemistry		x			x		x		x	x	x	
CA 19-9		x			x		x		x	x	x	
Urinalysis		x										
Pregnancy Test		x										
Tumor measurement	x								x	x		x
Concomitant Medications	x	➔	➔	➔	➔	➔	➔	➔	➔	➔	➔	➔
AE / SAE assessment		x	➔	➔	➔	➔	➔	➔	➔	➔	➔	➔
Survival status		x	➔	➔	➔	➔	➔	➔	➔	➔	➔	➔
Quality of life assessment		x										
Exploratory biomarker	x		x				x					
TAS-102 treatment			x (D1-5)	x (D8-12)			x (D1-5)	x (D8-12)				

Footnotes:

- (1) Sign ICF: Written informed consent should be obtained prior to the performance of any study procedure
- (2) Vital Signs: Heart rate, blood pressure, body temperature, respiratory rate; collect at the start of every cycle; collect within 24 hours prior to Day 1 study drug administration.
- (3) Blood tests within 28 days prior to study assessment include complete blood count, liver function test, renal function test, eGFR, coagulation profile & hepatitis B status.
- (4) Tumor Measurements: Obtain a contrast-enhanced computed tomography (CT) scan of the chest and abdomen (and pelvis, if clinically indicated) within 28 days prior to Day 1 of Cycle 1 and **every 8 weeks thereafter** during study treatment. If a patient discontinues treatment due to radiologic disease progression, additional tumor assessment is not required at the End of Treatment visit. For patients who discontinue treatment for reasons other than radiologic disease progression, every effort should be made to perform an end of treatment tumor assessment prior to the start of new anticancer therapy. Patients that discontinued treatment for reasons other than disease progression should continue to be followed for tumor response every 8 weeks until the patient develops radiologic disease progression (or death) or initiation of new anticancer therapy.

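### The protocol does not clearly keep scans on the start-of-treatment calendar after TAS-102 is stopped without radiologic progression, so the week-16 scan that decides the primary endpoint can be missed

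*Protocol*

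**What the plan says.** Section 7.2.12 of the Protocol opens by saying that tumor assessments "must be obtained at each time point listed below for all patients". After the baseline scan, the list gives three items that matter here:

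- "Every 8 weeks from the start of treatment";
- a scan "Within 2 weeks of the End of Treatment Visit if the patient has discontinued treatment for reasons other than radiologic disease progression";
- for those same patients, further scans "every 8 weeks during the follow-up period until the patient develops radiologic progression or the start of new anticancer treatment".

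The third item names no starting point for its 8 weeks.

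Appendix 1 covers the same ground differently. Its footnote 4 attaches the 8-weekly interval after baseline to the period of study treatment. For later scans it says: "Patients that discontinued treatment for reasons other than disease progression should continue to be followed for tumor response every 8 weeks". In the table, tumor measurement after treatment is marked in the survival follow-up column, under a block headed "End of Treatment Period (q8wk". Section 4 describes survival follow-up in similar terms: "At the end of treatment, all patients will be followed for survival at scheduled 8-week time intervals until 2 years".

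Section 7.1 allows CT scans a window of 7 days either way. Section 7.3 defines the primary outcome as being alive without RECIST progression 16 weeks after informed consent, and dates PFS at radiographic documentation of progression or at death. Section 9.3 sets the decision rule: the treatment passes if at least 6 of the first 25 evaluable patients are alive and progression-free at 16 weeks.

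**The concern.** The primary endpoint is status at one time point, so it depends on a scan at that time. On the start-of-treatment calendar a scan is due at week 16. If a site instead counts 8 weeks from the end-of-treatment scan, the sequence shifts. A patient scanned at end of treatment in week 10 is next due in week 18. Progression arising in between is seen and dated at week 18, and the patient is a success at week 16.

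The error has one direction: later detection can add apparent successes but cannot remove any. With a cut-off of 6 in 25, one patient can change the conclusion, and a scan that was never made cannot be recovered at analysis.

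**Working it through.** **1. The design as stated.** Inputs from section 9.3: null 10%, alternative 30%, type I error 0.05, power 80%, dropout 10%, at least 6 of 25.

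- P(X ≥ 6 | n = 25, p = 0.10) = 0.033
- P(X ≥ 6 | n = 25, p = 0.30) = 0.807
- 25 / 0.9 = 27.8, rounded up to 28

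The stated design reproduces, with the type I error taken as one-sided.

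**2. The passages side by side.**

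| Place | Points to the original calendar | Points to a new count |
|---|---|---|
| 7.2.12, lead-in and 8-weekly item | Counted from start of treatment, for all patients | – |
| 7.2.12, follow-up item | Says nothing of a restart | A separate item with its own 8 weeks and no anchor |
| Appendix 1, footnote 4 | Says patients continue to be followed | Ties the first interval to study treatment |
| Appendix 1, table | – | Later scans sit in the 8-weekly post-treatment block |

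Neither reading is excluded.

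**3. Which stopping times lose the week-16 scan, if the count restarts.** Let the end-of-treatment scan fall at week t after start of treatment; later scans fall at t + 8 and t + 16. With the 7-day window, a scan lies within a week of week 16 only if t is in 0-1, 7-9 or 15-16. That is 1 + 2 + 1 = 4 of 16 weeks. If stopping times were uniform (an assumption), 25% would keep a week-16 scan and 75% would not.

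**4. Effect on the 6-of-25 rule, if the count restarts.** Assumptions, none of them in the protocol:

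- exponential PFS, with weekly hazard λ = -ln(p)/16;
- a fraction f of patients assigned a stopping time uniform over weeks 0-16, unrelated to progression;
- all events found by scan;
- landmark and scans both counted from start of treatment.

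A patient with t > 8 is wrongly counted as a success if progression falls between t and 16. With t < 8, the interval is t + 8 to 16. In both cases the interval starts at a point uniform over weeks 8-16, so the added success rate per assigned patient is

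Δ = (e^(-8λ) - e^(-16λ)) / (8λ) - p.

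- p = 0.10: λ = 0.1439; Δ = (0.3162 - 0.1000) / 1.1513 - 0.1000 = 0.0878
- p = 0.30: λ = 0.0752; Δ = (0.5477 - 0.3000) / 0.6020 - 0.3000 = 0.1115

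The apparent 16-week rate is p + fΔ. The share who stop while unprogressed is f(1 - p)/(16λ), which is 0.391f at the null and 0.581f at the alternative.

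| f | Stop unprogressed, null | Apparent rate, null | P(pass), null | Apparent rate, alternative |
|---|---|---|---|---|
| 0 | 0 | 10.0% | 0.033 | 30.0% |
| 10% | 3.9% | 10.9% | 0.048 | 31.1% |
| 20% | 7.8% | 11.8% | 0.065 | 32.2% |
| 30% | 11.7% | 12.6% | 0.087 | 33.3% |

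A simulation of the same model agrees, giving 0.048 to 0.086. Because deaths are treated as scan-detected and nobody starts new therapy, the model leans high on those two counts.

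**The case against.** The strongest reply is that the protocol never states a restart. The scan list in 7.2.12 applies to all patients, its 8-weekly item counts from start of treatment, and the end-of-treatment and follow-up scans are further items in the same list. Footnote 4 speaks of continuing, which suits an unbroken calendar. The Appendix 1 heading also spans the end-of-treatment and 30-day safety visits, which are not 8-weekly, so it is weak evidence of an anchor; section 4 concerns survival, not imaging. This stands as far as it goes: the restart is an inference. It does not remove the restriction to study treatment in footnote 4, or supply an anchor for the follow-up scans.

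The second reply is that other rules protect the endpoint. Section 7.3.2 censors patients without progression at their last radiographic assessment, and section 9.3 excludes and replaces those who drop out before 16-week status can be assessed. Deaths are dated correctly whatever the calendar, and scanning stops at new anticancer therapy. Section 7.2.12 also asks for every effort to document objective progression after treatment stops. These points narrow the affected group considerably. They do not cover a patient who is still being scanned and whose progression is first documented after week 16: that patient has an event, is not a dropout, and counts as a success.

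A reader might infer that most early stoppers have no week-16 scan and are all carried past the landmark as progression-free. The documents do not support that. They give neither the number nor the timing of early stops, and the 75% in step 3 needs both an assumed restart and uniform stopping. Nor does every stop after week 8 miss the window: an end-of-treatment scan at week 8.5 puts the next at 16.5, within 7 days. A reader might also take one or two of the 25 as certain false successes, which would put the null pass probability at P(X ≥ 5 | 24, 0.10) = 0.085 or P(X ≥ 4 | 23, 0.10) = 0.193. Certainty is not justified. Even over a 6-week gap, the same exponential model gives a 58% chance of an event at the null rate and 36% at the alternative, and those figures include deaths, which are not misdated.

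**Conclusion.** The point holds as an ambiguity with consequences for the primary endpoint, not as a stated restart. Three places describe scans after early discontinuation, and together they let a site move off the week-16 time point. Where that happens, the bias favours rejecting the null and is limited to patients who stop unprogressed, start no new therapy, survive past week 16 and are scanned later.

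The size is conditional. With an assumed restart and 10-30% of patients assigned an early stop, the apparent null rate is 10.9-12.6% and the null pass probability about 0.05-0.09, against 0.033 as designed and the stated 0.05. If sites keep the original calendar, this bias does not arise. Severity is moderate: the wording should be settled before scans are lost, but the design is not shown to fail.

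**What to change.** Reconcile section 7.2.12, footnote 4 and the Appendix 1 table so that all three say:

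- after treatment stops without radiologic progression, tumor assessments stay on the original 8-weekly calendar (weeks 8, 16, 24 and so on, within 7 days) until radiologic progression or new anticancer therapy;
- the end-of-treatment scan is additional and does not reset the calendar, but may serve as a scheduled scan if it falls in that window.

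The calendar should also use the same time origin as the 16-week endpoint. At present the endpoint runs from informed consent, which Appendix 1 places in the day -28 to -1 column, while scans run from start of treatment. The landmark can therefore precede the week-16 scan for any patient, including those still on treatment. That is a separate matter, but unless it is settled the clarified calendar will not secure a scan at the landmark.

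The scan-calendar clarification costs a wording amendment. The 8-week interval is unchanged, and the follow-up scans of a patient whose site would have restarted the count move back to the original dates. Aligning the time origin is a further amendment, to either the endpoint definition or the scan calendar.
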